9.6 Adverse events for special monitoring

UCB has identified AEs for special monitoring (AESM). An AESM is an AE or safety topic for which special monitoring, additional data collection activities, and/or enhanced signal detection activities (within UCB), are considered appropriate. Identified AESM can be of particular interest based on findings from the IMP clinical program to date, potential risks generally associated with biologic immunomodulators, or comorbidities and risk factors prevalent in the study population.

Adverse events for special monitoring for this study include: serious infections (including opportunistic infections and TB; see [Section 9.8.1](#)), cytopenias, hypersensitivities, suicide ideation or behavior (assessed using the eC-SSRS; see [Section 9.8.6](#)), depression and anxiety (assessed using the HADS; see [Section 12.9](#)), major cardiovascular events, and liver function test changes/enzyme elevations (ALT, AST, bilirubin; see [Section 9.7.1](#)), malignancies, and inflammatory bowel diseases.

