3.11 Changes to protocol-defined analyses

There have been no changes to the protocol-defined analyses.

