- Incidence of TEAEs by Relationship, SOC, HLT and PT
- Incidence of Non-Serious TEAEs by Relationship, SOC, HLT and PT
- Incidence of Non-Serious TEAEs Above Reporting Threshold of 5% by Relationship, SOC and PT
- Incidence of Serious TEAEs per 100 subject years by SOC, HLT and PT
- Incidence of Serious TEAEs by Relationship, SOC, HLT and PT
- Incidence of TEAEs Leading to Discontinuation by SOC, HLT and PT
- Incidence of TEAEs Leading to Death by SOC, HLT and PT
- Incidence of TEAEs Leading to Death by Relationship, SOC, HLT and PT

The incidence of serious TEAEs per 100 subject years will also be summarized for PS0010 and PS0011 combined, where treatment emergence and exposure at risk are relative to the first dose of study drug in PS0010. In the case of a subject that switches study treatment when starting PS0011, exposure at risk to PS0010 treatment will end the day prior to the first PS0011 dose. Adverse events that occur on the PS0011 baseline visit date will be attributed to the PS0010 treatment. The only exception to this definition is for the following types of events:

- Those that code to a High Level Term (HLT) of “Injection Site Reactions”
- Those which have been designated as an Injection Reaction on the AE CRF and do not code to a System Organ Class (SOC) of “Investigations”
- Those which have been identified as a hypersensitivity reaction or an anaphylactic reaction

When any of these events occur on the date of treatment switch at PS0011 Baseline, the AE will be attributed to the treatment initiated in PS0011.

The following by-subject listings will be provided:

- All serious TEAEs
- All TEAEs leading to discontinuation of study treatment

- All death data
- All TEAEs and all non-TEAEs
- All treatment-emergent adverse drug reactions
- All AEs of special monitoring (AESM).

The following are AESM that require special statistical analyses:

1. Serious infections, opportunistic infections including TB and fungal infections

Serious infections will be identified based on MedDRA classification (SOC “Infections and infestations”) using the “Any SAE” table. A separate table does not need to be produced to summarize these events.

Fungal infections will be summarized in a stand-alone table which presents EAIR and EAER. The table will include all TEAEs which code into the high level group term (HLGT) of “Fungal infectious disorders”.

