b) Anaphylactic reactions

An algorithmic approach will be used to identify TEAEs that are considered to be anaphylactic reactions. PTs are separated into the four distinct categories (A, B, C, D) prior to the algorithmic approach being applied.

All TEAEs that either emerged on the same day as when a study medication injection reaction was received, or that emerged one day after a study medication injection was received, and which fulfill any of the three criteria described in [Section 12.3](#) will be included in the summary table.

8. Hepatic events and DILI

Although not officially considered to be AEs of special monitoring, hepatic events are nonetheless considered to be interesting enough to be summarized in stand-alone tables.

Hepatic events will be summarized in a stand-alone table that includes all TEAEs in the SMQ “Drug related hepatic disorders – comprehensive search (SMQ)”. Note that the following two sub-SMQs are to be excluded: “Liver neoplasms, benign (incl cysts and polyps)” and “Liver neoplasms, malignant and unspecified (SMQ)”.

The SMQ search should include all TEAEs (regardless of whether they have been judged as related to study medication or not) which code to a PT included in the Scope = Narrow group within each SMQ.

Hy’s Law cases are to be reported separately in the liver function test summary table (with adjudication for “Potential drug-induced liver injury” cases).

Additional tables will summarize TEAEs by responder status (defined as PS0010 Week 12 PASI90 response):

- Incidence of TEAEs – Overview
- Incidence of TEAEs per 100 subject years by SOC, HLT and PT
- Incidence of Serious TEAEs per 100 subject years by SOC, HLT and PT
- Incidence of Fungal Infectious Disorders per 100 subject years by SOC, HLT and PT

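### The SAP disclaims the special-monitoring status that the protocol gives to liver events, leaving their place in the AESM listing unclear, and its stand-alone hepatic table specifies no pooled exposure-adjusted rate

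*SAP*

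**What the plan says.** Protocol 9.6 lists the AESM topics for this study. The list includes "major cardiovascular events, and liver function test changes/enzyme elevations (ALT, AST, bilirubin", with a cross-reference to the section on potential drug-induced liver injury (PDILI).

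SAP 8.2.1 plans a by-subject listing described only as "All AEs of special monitoring (AESM"), and a separate one of "All TEAEs and all non-TEAEs". It then opens an eight-item list with "The following are AESM that require special statistical analyses". Item 8 of that list is hepatic events, and it begins: "Although not officially considered to be AEs of special monitoring, hepatic events are nonetheless considered to be interesting enough" to have tables of their own. The table itself is specified as follows: "Hepatic events will be summarized in a stand-alone table that includes all TEAEs in the SMQ" for drug-related hepatic disorders, narrow scope, with two liver-neoplasm sub-queries removed. Neither EAIR nor EAER is mentioned.

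SAP 3.11 states: "There have been no changes to the protocol-defined analyses".

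SAP 8.1.6 gives every TEAE an EAIR with 95% confidence interval and an EAER by SOC, HLT and PT.

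**The concern.** Two documents that should agree on which safety topics are specially monitored do not, and the SAP gives no reason. The SAP also disagrees with itself, since the disclaimer stands under an AESM heading. A programmer who follows the text of item 8 leaves hepatic events out of the AESM listing. One who follows the heading puts them in.

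The second issue is the hepatic table. The primary objective is long-term safety, and the primary variable is TEAE incidence adjusted for exposure. The adjustment matters because subjects without a PASI75 response at Week 12 or later are withdrawn, so time at risk depends on response and may differ by dose group. A hepatic table showing only counts and percentages lacks that protection for the grouped event.

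**Working it through.** **1. AESM status, side by side.**

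| Place | What it implies for liver events |
|---|---|
| Protocol 9.6 | AESM, named expressly |
| SAP 8.2.1, heading over items 1 to 8 | AESM |
| SAP 8.2.1, item 8 text | not officially AESM |
| SAP 8.2.1, AESM listing | membership not stated |
| SAP 3.11 | no departure declared |

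The first two rows cannot be squared with the third. Inclusion in the listing is therefore undefined; exclusion is the literal reading of item 8.

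**2. Which stand-alone tables specify EAIR and EAER.**

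| Item in SAP 8.2.1 | Specified? |
|---|---|
| 1 Fungal and opportunistic infections | yes |
| 2 Malignancies | yes |
| 3 Major cardiovascular events | yes |
| 4 Cytopenias | no |
| 5 Neuropsychiatric events | yes |
| 6 Inflammatory bowel disease | yes |
| 7 Anaphylactic/hypersensitivity reactions | no |
| 8 Hepatic events | no |

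Items 4 and 7 carry no disclaimer of AESM status, yet they lack the rates too. The disclaimer in item 8 therefore does not explain the gap.

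**3. Can a pooled hepatic rate be recovered from the primary table?**

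*EAER* (SAP 8.1.5, equation 13): 100 × number of events / total time at risk. The denominator is the same for every PT within a treatment group, so the PT-level EAERs of the hepatic terms can be added. The pooled EAER is recoverable.

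*EAIR* (SAP 8.1.4, equation 10): 100 × n / summed time, where n counts subjects and each affected subject's time stops at the first occurrence of the AE in question. Take a subject with hepatic terms A and B. The PT rows count that subject once under A and once under B, each with time stopped at a different date. The pooled rate counts the subject once, with time stopped at the earlier date. The PT rows show neither the overlap nor the earlier date, so the pooled EAIR and its interval cannot be derived from them.

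**4. How much can crude percentages mislead?**

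Time at risk is last dose minus first dose plus 140 days (SAP 8.1.3, equation 7).

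- Week 12 PASI75 failure, taken as last dosed at Week 8: 56 + 140 = 196 days.
- Completer, with 24 injections at two per visit (SAP 7), so 12 doses and the last at Week 44: 308 + 140 = 448 days.
- Ratio: 448 / 196 = 2.3.

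Let *f* be the fraction withdrawn at Week 12, and assume a constant true rate of 0.05 per subject-year in every group. The expected crude incidence is

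(1 − *f*)(1 − exp(−0.05 × 448/365.25)) + *f*(1 − exp(−0.05 × 196/365.25)) = (1 − *f*) × 0.05949 + *f* × 0.02647

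| *f* | Crude incidence |
|---|---|
| 0 | 5.95% |
| 0.1 | 5.62% |
| 0.3 | 4.96% |

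The widest gap is 5.95 − 4.96 = 0.99 percentage points, or 0.99 / 5.95 = 17% in relative terms. The relative figure depends little on the assumed rate. For rare events, crude incidence is nearly proportional to mean time at risk, and (0.7 × 448 + 0.3 × 196) / 448 = 372.4 / 448 = 0.83, again about 17% lower.

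**The case against.** The strongest reply is that little is lost. All adverse events are listed by subject, whether or not they are labelled AESM. Hepatic terms have exposure-adjusted rates in the primary table, and also in the combined PS0010/PS0011 and responder-status tables. The protocol uses AESM as a monitoring and signal-detection label, promises no exposure-adjusted rate for AESM groups, and in section 14.3.2 leaves further AE summaries to the SAP. All of this stands, and a pooled EAIR is therefore an improvement to the plan and not a promise broken.

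A second reply is that the texts cover different things: the protocol topic is laboratory change, while item 8 is a hepatic-disorder query on reported events. Liver laboratory values have by-visit, shift, markedly abnormal and potential Hy's Law summaries in SAP 8.2.2. This stands in part. Those summaries give statistics, counts or percentages without exposure adjustment. The marked-abnormality limit for ALT and AST is 5 × ULN, and the Hy's Law table also requires raised bilirubin. The protocol's PDILI criteria begin at 3 × ULN (sections 6.3.1 and 9.7.1), and section 9.7.1 requires every PDILI event to be reported as an AE. Isolated elevations between 3 and 5 × ULN are singled out in neither laboratory summary, so the hepatic AE table has work of its own to do.

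A third reply is that the 17% is hypothetical, and it is. Neither document gives a hepatic event rate or a withdrawal fraction. The study is non-randomised and descriptive, with up to 240 subjects, and the gap is about one subject per 100.

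**Conclusion.** The point holds in a limited form. Protocol and SAP conflict on whether liver events are AESM, the SAP conflicts with itself, and SAP 3.11 does not acknowledge it. Separately, no pooled EAIR with confidence interval is specified for hepatic events, and none can be derived from the planned rows.

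Three stronger readings are tempting, and the documents do not support them. A reader might infer that hepatic events get no exposure-adjusted rate at all; SAP 8.1.6 gives them rates at SOC, HLT and PT level, and the pooled EAER follows by addition. A reader might infer that the rate is missing because hepatic events were denied AESM status; cytopenias and anaphylactic/hypersensitivity reactions lack it as well. A reader might infer that the AESM listing certainly omits hepatic events; its membership is undefined, and the heading above item 8 points the other way.

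The distortion in crude percentages is up to about 1 percentage point. It rests on an assumed common rate of 5 per 100 subject-years, an assumed contrast of 0% and 30% Week 12 withdrawal, and last doses at Weeks 8 and 44. It shows direction and scale and predicts nothing. The primary analysis is not threatened, but the correction is worth making because it is nearly free and serves the primary objective.

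**What to change.** In SAP 8.2.1 item 8, delete the clause saying that hepatic events are not officially AESM. State instead that they are AESM under protocol 9.6 and enter the by-subject AESM listing. If a departure from the protocol was intended, record it with its reason in SAP 3.11.

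Add EAIR with 95% confidence interval and EAER to the stand-alone hepatic table, including an overall row for any hepatic event in which each subject's time stops at the first such event. Do the same for cytopenias (item 4) and anaphylactic/hypersensitivity reactions (item 7), so that all stand-alone AESM tables follow one rule.

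The cost is a few SAP sentences and extra columns in three tables. The derivations are already in SAP 8.1.4 and 8.1.5, and no new data are needed.

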8.2.2 Clinical laboratory evaluations

All laboratory data recorded in the electronic case report form (eCRF) will be summarized. If any additional analytes to those in [Table 8-1](#) are also recorded then these will be listed only.

Table 8-1: Laboratory measurements

Hematology	Chemistry	Urinalysis
Basophils	Calcium	Albumin

Hematology	Chemistry	Urinalysis
Eosinophils	Chloride	Bacteria
Lymphocytes	C-reactive protein	Crystals
Monocytes	Magnesium	Glucose
Neutrophils	Potassium	pH
Hematocrit	Sodium	Red blood cell
Hemoglobin	Glucose	White blood cell (WBC)
Mean corpuscular hemoglobin	Blood urea nitrogen	Urine dipstick for pregnancy testing ^a
Mean corpuscular hemoglobin concentration	Creatinine	
Mean corpuscular volume	Alkaline phosphatase	
Platelet count	Aspartate aminotransferase (AST)	
Red blood cell count	Alanine aminotransferase (ALT)	
White blood cell count	Gamma glutamyltransferase (GGT)	
	Total bilirubin	
	Lactate dehydrogenase	
	Total cholesterol	
	Serum pregnancy testing ^a	

^a Pregnancy testing will be done in all women of childbearing potential and will consist of serum testing at the Safety Follow-Up visit and urine testing at all other visits.

For tables where data are summarized by visit, unscheduled and repeat visits will not be summarized, but these data will be included in listings. For tables where multiple measurements over a period of time are considered (as in shift tables), unscheduled and repeat visits will be considered as long as they were collected during the treatment period. All summaries will be presented in International System of units and will be based on observed case values. In the case where laboratory values are below the lower limit of quantification, then these will be set to the midpoint between zero and the lower limit of quantification for the purpose of summarizing the data.

The change from Baseline tables will be presented using descriptive statistics by PS0011 treatment group. The table presentations will display descriptive statistics for the PS0011 Baseline followed by descriptive statistics for the change from PS0011 Baseline results by scheduled visit for PS0011.

The following summaries will be provided:

- The observed and change from Baseline values in each laboratory variable by PS0011 treatment group and visit

- The number and percentage of subjects experiencing markedly abnormal values by laboratory variable, PS0011 treatment group and visit
- A shift table of the number and percentage of subjects experiencing low, normal or high values at Baseline to maximum post-Baseline value (ie, low, normal, high), by laboratory variable and PS0011 treatment group
- A shift table of the number and percentage of subjects experiencing low, normal or high values at Baseline to minimum post-Baseline value (ie, low, normal, high), by laboratory variable and PS0011 treatment group
- A shift table of the number and percentage of subjects experiencing low, normal or high values at Baseline to the End of Treatment¹ value (ie, low, normal, high), by laboratory variable and PS0011 treatment group.

¹The End of Treatment value refers to the value from the last observed non-missing post baseline visit prior to the end of treatment.

A by-subject listing of all laboratory data will be provided. This listing will be presented by PS0011 treatment group and will include: center, subject identifier, age, gender, race, weight, visit, laboratory variable, result (with abnormal values flagged as “L” or “H” accordingly) and unit.

A summary table highlighting the potential cases of Hy’s Law within each PS0011 treatment group will be presented. Hy’s Law is defined as:

- AST > 3xULN or ALT >3xULN and
- Total Bilirubin ≥2xULN.

Markedly abnormal values are defined as those with a severity of Grade 3 and above based on the common terminology criteria for adverse events criteria (U.S. Department of Health and Human Services 2010). The markedly abnormal laboratory data will be summarized by visit and for any visit while on treatment. Definitions of markedly abnormal values using the Grade 3 cutpoints are given in the tables below for age ranges of ≥ 17 years ([Table 8-2](#) for markedly abnormal liver function test values, [Table 8-3](#) for markedly abnormal hematology values and [Table 8-4](#) for markedly abnormal biochemistry values). The laboratory results classified as Grade 3 or 4 will be listed separately.

Table 8–2: Definitions of Marked Abnormal Liver Function Tests

Parameter name	Conventional		Standard		Abnormal Designation
	Unit	Criteria	Unit	Criteria	
Alkaline Phosphatase		≥5.0 x ULN		≥5.0 x ULN	AH
ALT	U/L	≥5.0 x ULN	U/L	≥5.0 x ULN	AH
AST	U/L	≥5.0 x ULN	U/L	≥5.0 x ULN	AH
Total Bilirubin	mg/dL	≥3.0 x ULN	umol/L	≥3.0 x ULN	AH
GGT	U/L	≥5.0 x ULN	U/L	≥5.0 x ULN	AH

Table 8–3: Definitions of Marked Abnormal Clinical Chemistry Values

Parameter name	Conventional		Standard		Abnormal Designation
	Unit	Criteria	Unit	Criteria	
Albumin	g/dL	<2.0	g/L	<20	AL
Creatinine	mg/dL	>3.0 x ULN	umol/L	>3.0 x ULN	AH
Glucose	mg/dL	<30 >250	umol/L	<1.7 >13.9	AL AH
Calcium	mg/dL	<7.0 >12.5	umol/L	<1.75 >12.5	AL AH
Magnesium	mg/dL	<0.9 >3.0	umol/L	<0.4 >1.23	AL AH
Potassium	umol/L	<3.0 >6.0	umol/L	<3.0 >6.0	AL AH
Sodium	umol/L	<130 >155	umol/L	<130 >155	AL AH
Total Cholesterol	mg/dL	>400	umol/L	>10.34	AH

Table 8–4: Definitions of Marked Abnormal Hematology Values

Parameter name	Conventional		Standard		Abnormal Designation
	Unit	Criteria	Unit	Criteria	
Hemoglobin	g/dL	<8.0 >4.0 above ULN	g/L	<80 >40 above ULN	AL AH
Lymphocytes Absolute	10 ⁹ /L	<0.5 >20.0	10 ⁹ /L	<0.5 >20.0	AL AH
Neutrophils Absolute	10 ⁹ /L	<1.0	10 ⁹ /L	<1.0	AL
Platelets	10 ⁹ /L	<50	10 ⁹ /L	<50	AL
WBC/Leukocytes	10 ⁹ /L	<2.0 >100	10 ⁹ /L	<2.0 >100	AL AH

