9.5 Adverse events of special interest

An AE of special interest is any AE that a regulatory authority has mandated be reported on an expedited basis, regardless of the seriousness, expectedness, or relatedness of the AE to the administration of a UCB product/compound.

Potential Hy’s Law, defined as $\geq 3 \times \text{ULN}$ ALT or AST with coexisting $\geq 2 \times \text{ULN}$ total bilirubin in the absence of $\geq 2 \times \text{ULN}$ ALP, with no alternative explanation for the biochemical abnormality, must ALWAYS be reported to UCB as an AE of special interest (ie, without waiting for any additional etiologic investigations to have been concluded). Follow-up information should then

be reported if an alternative etiology is identified during investigation and monitoring of the subject.

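### The SAP's Hy's Law rule (strict >3xULN, no ALP condition, coexistence not stated) differs from Protocol 9.5, so the summary table may not reconcile with the reported events of special interest

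*SAP*

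**What the plan says.** SAP 8.2.2 (Clinical laboratory evaluations) announces the table: "A summary table highlighting the potential cases of Hy’s Law within each PS0011 treatment group will be presented". The definition has two lines: "AST > 3xULN or ALT >3xULN and" then "Total Bilirubin ≥2xULN". It mentions neither ALP nor timing. SAP 8.2.1, under hepatic events, sends Hy's Law cases to the liver function table "with adjudication for “Potential drug-induced liver injury” cases" and gives no adjudication criteria or process.

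Protocol 9.5 (Adverse events of special interest) reads "Potential Hy’s Law, defined as $\geq 3 \times \text{ULN}$ ALT or AST with coexisting", followed by a level of at least 2xULN for "total bilirubin in the absence of $\geq 2 \times \text{ULN}$ ALP, with no alternative explanation for the biochemical abnormality". Such a case "must ALWAYS be reported to UCB as an AE of special interest", before the search for a cause is complete. Protocol 9.7.1 repeats this duty for potential drug-induced liver injury (PDILI) events.

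Protocol 6.3.1 has a separate PDILI criterion: ALT or AST of at least 3xULN with coexisting total bilirubin of at least 2xULN, without an ALP condition. SAP 3.11 declares no departures from the protocol's analyses.

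**The concern.** Potential Hy's Law is the only event that Protocol 9.5 names as an adverse event of special interest, and the study's primary objective is long-term safety. The liver function table is the only SAP summary specific to it. If the table and the protocol use different rules, a reader comparing the table with the reported events could find a case in one and not in the other, with nothing in the SAP to explain it. Such cases are few and each is read closely, so a discrepancy of one would need explaining.

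**Working it through.** The study is descriptive (Protocol 14.2) and the plan gives no figure to reproduce. The check is a comparison of two logical rules.

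**Rules, in multiples of ULN**
- Protocol 9.5, laboratory part: max(ALT, AST) ≥ 3, coexisting bilirubin ≥ 2, and not ALP ≥ 2.
- SAP 8.2.2: max(ALT, AST) > 3 and bilirubin ≥ 2. Timing is not stated, so it was run two ways: elevations at any time, and elevations in the same sample.

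**Condition by condition**

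| Condition | Protocol 9.5 | SAP 8.2.2 |
|---|---|---|
| ALT or AST | ≥3 | >3 |
| Total bilirubin | ≥2 | ≥2 |
| Timing | coexisting | not stated |
| ALP | must not be ≥2 | not mentioned |
| Alternative explanation | must be absent | not mentioned; adjudication noted in 8.2.1 without criteria |

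**Illustrative profiles** (AST is 1 throughout; for this check, coexisting was coded as the same visit)

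| Profile | Protocol | SAP, any time | SAP, same sample |
|---|---|---|---|
| A: ALT 4, bilirubin 2.5, ALP 1 | yes | yes | yes |
| B: ALT exactly 3, bilirubin 2.5, ALP 1 | yes | no | no |
| C: ALT 4, bilirubin 2.5, ALP 2.5 | no | yes | yes |
| D: ALT 4 at one visit, bilirubin 2.5 at another | no | yes | no |
| E: ALT 2.9, bilirubin 2.5, ALP 1 | no | no | no |
| F: ALT 4, bilirubin exactly 2, ALP 1 | yes | yes | yes |
| G: ALT 4, bilirubin 2.5, ALP exactly 2 | no | yes | yes |

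The rules agree on A, E and F. They disagree on B, C and G under either reading of the SAP, and in both directions: B is missed by the SAP, while C and G are added. D depends on a timing rule that the SAP does not give. With the SAP's laboratory criteria aligned to Protocol 9.5, all seven profiles are classified alike. The alternative-explanation condition cannot be derived from laboratory values and needs medical review.

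**Does other text settle it?**
- The Protocol 6.3.1 criterion also lacks an ALP condition, but it uses ≥3xULN and requires coexistence. The SAP rule therefore matches neither protocol definition.
- SAP Table 8-2, in the same section, uses ≥ for its multiples of ULN in liver tests. No reason is given for the strict inequality in the Hy's Law rule.
- ALP is among the analytes in SAP Table 8-1, so its absence from the rule is not a data limitation.

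**The case against.** The strongest reply is that the table is a deliberately broad screen for potential cases, with adjudication to follow. Leaving ALP out parallels Protocol 6.3.1, and a footnote to Protocol Table 9-3 sends raised ALP to discussion with the Medical Monitor rather than excluding the case. The strict inequality matters only if a subject's qualifying transaminase values reach exactly 3xULN and never exceed it, and repeat testing gives further chances to exceed it. Such a subject also stays visible: PDILI events are reported as AEs, hepatic events have their own table, and all laboratory data are listed. Finally, Protocol 14.3.2 defines no Hy's Law table, so the SAP replaces no protocol-defined analysis.

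Much of this stands. Under-inclusion is a boundary case, over-inclusion is the larger effect, and SAP 3.11 is not clearly contradicted. But a screen plus adjudication reconciles with Protocol 9.5 only if the SAP says what adjudication decides, which it does not. Adjudication confined to flagged cases cannot recover one left out at exactly 3xULN.

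Two stronger readings are tempting. A reader might infer that the SAP will flag subjects whose ALT and bilirubin peaks are months apart. That follows only if elevations at any time are allowed, and the SAP does not say so; this is an ambiguity rather than a stated rule. A reader might also infer that both elevations must come from one sample. The protocol says coexisting. It also provides for local and central samples and for monitoring at least twice a week, so a strict same-sample rule could drop a case that the protocol counts.

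**Conclusion.** The definitions differ, and the SAP neither declares nor explains the difference. Two departures are certain from the text: a value of exactly 3xULN is missed, and cases with ALP at or above 2xULN are counted. A third, timing, is an omission whose effect depends on how it is programmed. The protocol's fourth condition, "with no alternative explanation for the biochemical abnormality", has no stated counterpart beyond the undefined adjudication.

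The consequence is limited to one descriptive table and its reconciliation with the reported events. A reader might infer that safety reports would be lost or created, but sites report under Protocol 9.5 and 9.7.1, which the SAP does not alter. Nor does it follow that the counts will differ: that needs a boundary, high-ALP or non-coexisting case to occur. The documents give no frequency for these. For scale only, an assumed 0 to 3 of up to 240 subjects is 0% to 1.25% (3/240 = 0.0125). The primary variable, exposure-adjusted TEAE incidence, does not use this rule. The change should be made because it is nearly free and each such case is important.

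**What to change.** In SAP 8.2.2:
1. Align the laboratory criteria with Protocol 9.5: ALT or AST ≥3xULN, coexisting total bilirubin ≥2xULN, and ALP not ≥2xULN.
2. State how coexisting is operationalized, for example as a declared window, which need not mean the same sample.
3. Show cases that meet the transaminase and bilirubin criteria but have ALP ≥2xULN in a separate row, so that none disappears from view.
4. State that the alternative-explanation condition is applied through the adjudication mentioned in SAP 8.2.1, and give its criteria.

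If the sponsor prefers a broader screen, the SAP should declare and justify the departure in 3.11. The cost is a few lines of SAP text and a timing condition in the program. No new data are needed, and no clinical rule changes.

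### SAP Table 8-3 carries the mg/dL figure for markedly high calcium unconverted into the standard-unit column (12.5 instead of about 3.12 mmol/L), and labels six analytes umol/L whose figures are mmol/L values

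*SAP*

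**What the plan says.** Section 8.2.2 of the SAP sets the rule: "Markedly abnormal values are defined as those with a severity of Grade 3 and above", with reference to the CTCAE. It adds that "Definitions of markedly abnormal values using the Grade 3 cutpoints are given in the tables below". The output these cuts feed is listed in the same section: "The number and percentage of subjects experiencing markedly abnormal values by laboratory variable, PS0011 treatment group and visit". On units, the section says "All summaries will be presented in International System of units and will be based on observed case values".

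Table 8-3, titled "Definitions of Marked Abnormal Clinical Chemistry Values", gives each analyte a conventional unit and cut and a standard unit and cut. For calcium the conventional pair is below 7.0 / above 12.5 mg/dL, and the standard pair is below 1.75 / above 12.5, labelled umol/L. The standard unit is also printed umol/L for glucose, magnesium, potassium, sodium and total cholesterol. Potassium and sodium carry umol/L in the conventional column as well.

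The text introducing the tables assigns Table 8-3 to hematology and Table 8-4 to biochemistry. The titles are the other way round: Table 8-4 is "Definitions of Marked Abnormal Hematology Values".

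The amendment log in SAP Section 13 records a change to Table 8-1 in this section but none to Table 8-3, so this is current text.

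**The concern.** The two columns of Table 8-3 are meant to express one threshold in two unit systems. For high calcium they cannot: a single unit conversion cannot take 7.0 to 1.75 and also leave 12.5 at 12.5. The cell therefore contradicts the one beside it, and with it the statement that the tables give the Grade 3 cuts.

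The SAP does not say which column drives flagging, but because summaries are in SI units the standard column is the likelier one. If it is used with calcium in mmol/L, the high-calcium row misses everything between about 12.5 and 50 mg/dL. The result is a row of zeros that looks like reassuring safety data, in a study whose primary objective is long-term safety and which draws biochemistry at every visit. Protocol Section 6.3, criterion 9, withdraws subjects with Grade 3 or higher laboratory values, so a subject withdrawn for high calcium could be absent from the SAP table meant to show such values.

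The unit labels are a separate fault. They do no harm if the programmer reads the figures as mmol/L, but the printed label does not say so.

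**Working it through.** **Inputs.** All cuts are from SAP Table 8-3. The molar masses (g/mol) are physical constants, not figures from the documents: calcium 40.078, magnesium 24.305, glucose 180.156, cholesterol 386.65. The calcium result does not depend on them, because the row supplies its own factor.

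**Formula.** mmol/L = mg/dL × 10 / molar mass; umol/L = 1000 × mmol/L.

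**Calcium from the table alone.** The low pair gives 1.75 / 7.0 = 0.25. Applied to the high cut, 12.5 × 0.25 = 3.125. By molar mass:
- Low: 7.0 × 10 / 40.078 = 1.747 (printed 1.75; agrees).
- High: 12.5 × 10 / 40.078 = 3.119 (printed 12.5; does not agree).
- Ratio for the high cut: 12.5 / 3.119 = 4.0.

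**All eleven standard-column cuts for the six analytes, read as mmol/L.**

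| Analyte, cut | Conventional column | Converted to mmol/L | Printed standard figure |
|---|---|---|---|
| Glucose, low | 30 mg/dL | 1.67 | 1.7 |
| Glucose, high | 250 mg/dL | 13.88 | 13.9 |
| Calcium, low | 7.0 mg/dL | 1.75 | 1.75 |
| **Calcium, high** | **12.5 mg/dL** | **3.12** | **12.5** |
| Magnesium, low | 0.9 mg/dL | 0.37 | 0.4 |
| Magnesium, high | 3.0 mg/dL | 1.23 | 1.23 |
| Total cholesterol, high | 400 mg/dL | 10.345 | 10.34 |
| Potassium, low and high | 3.0, 6.0 | same figures in both columns | 3.0, 6.0 |
| Sodium, low and high | 130, 155 | same figures in both columns | 130, 155 |

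Ten of the eleven agree to rounding, and only high calcium fails. Six of the ten are true conversions. The four potassium and sodium cuts simply repeat across the columns, and they are plausible serum values only as mmol/L.

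**The unit label.** In umol/L each converted figure would be 1000 times larger; glucose, for example, would be about 1665 and 13877. The printed 1.7 and 13.9 are therefore mmol/L values. Creatinine is also labelled umol/L, but its cut is a multiple of the upper limit of normal, so nothing depends on the label there. The labels to change are six in the standard column plus two (potassium, sodium) in the conventional column, eight in all.

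**Consequence under each reading of the standard column.**
- As mmol/L: 12.5 × 40.078 / 10 = 50.1 mg/dL. High-calcium values between about 12.5 and 50 mg/dL are not flagged; the other ten cuts work as intended.
- Literally as umol/L: 12.5 umol/L = 0.0125 mmol/L, and 0.0125 × 40.078 / 10 = 0.05 mg/dL, so every calcium value is flagged high. The same happens to all six high cuts, while all five low cuts flag no one.

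**The case against.** The strongest counter-argument is that the practical effect is very small. The documents give no expected rate of high calcium, and calcium is not among the topics for special monitoring. A high value would still appear in the laboratory listing with its H flag, in the shift table to maximum post-Baseline value and in the maxima of the observed-value summaries. Under protocol Section 6.3 a Grade 3 value also leads to withdrawal, independently of the SAP table. All of this stands and is why the point is minor. It does not make the threshold right: the table designed to count such values would still not count them.

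A second argument is that the literal umol/L result is unrealistic, because a table showing every subject markedly high for six analytes would be caught at once. That is fair. The reading that matters is the mmol/L one, where the failure is silent.

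A third is that the figure to print is debatable. The cuts are tied to an external grading standard, other rows use one decimal, and the magnesium low cut is rounded more coarsely (0.4 against 0.37) than 3.1 would be for calcium. It is true that 3.1 would be far closer than 12.5. But 3.12 is the direct conversion of the SAP's own 12.5 mg/dL at the precision of that row's low limit. It corresponds to 12.48 mg/dL by the row factor and 12.50 by molar mass, while 3.1 corresponds to 12.40 to 12.42.

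Finally, the unit labels and the swapped table references are editorial, since row names and table titles are clear. That is also true, and they are listed only because they sit in the same place and can be corrected together.

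**Conclusion.** The point holds. The standard-column cut for markedly high calcium is the mg/dL figure unconverted. It should be about 3.12 mmol/L, so the printed value is 4.0 times too high when read as mmol/L. One number, eight unit labels and one pair of table references are wrong, and the SAP amendment corrects none of them.

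Severity is minor. The damage is limited to the markedly-abnormal laboratory table and to any separate Grade 3/4 listing programmed from the same cuts. Shift tables, L/H flags, change-from-Baseline summaries, withdrawal decisions and the primary analysis of treatment-emergent adverse events do not use Table 8-3.

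The stated consequence assumes that flagging uses the standard column with calcium held in mmol/L. That is likely, given "All summaries will be presented in International System of units", but the SAP does not say so. If flagging uses the mg/dL column, the high-calcium row is unaffected. The check covers agreement between the two columns only, not whether the cuts match the cited CTCAE grades.

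**What to change.** In SAP Section 8.2.2:

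1. In Table 8-3, standard column, replace the calcium upper cut of above 12.5 with above 3.12 mmol/L, keeping two decimals as in the row's low limit.
2. Relabel glucose, calcium, magnesium, potassium, sodium and total cholesterol as mmol/L in the standard column, and potassium and sodium as mmol/L in the conventional column too.
3. State that flagging uses the standard column.
4. Correct the table references so that Table 8-3 is biochemistry and Table 8-4 is hematology.

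The cost is a minor SAP correction: one table, a sentence on flagging, one cross-reference and one programming constant. No additional data are needed.
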